## 5 Treatment

### 5.1 Treating the patient

The Investigator needs to instruct the patient to take the study drug as per protocol. All dosages prescribed and dispensed to the patient and all dose changes during the study must be recorded on the Dosage Administration Record eCRF.

#### 5.1.1 Administration

**Table 5-1 Treatment and treatment schedule**

Study treatment	Pharmaceutical form and route of administration	Dose	Frequency
INC424	Tablets for oral use	Starting dose 5 mg to be increased or decreased (5 mg steps) per Bayesian design (see Section 5.1.2 )	b.i.d. (approximately 12 hours apart: morning and night)

Patients will self-administer INC424 tablets as instructed (see [Table 5-1](#) and [Section 5.1.2](#)). If the patient forgets to take a dose, then he/she should take INC424 within 3 hours after the missed dose. If more than 3 hours have passed, then that missed dose should be omitted and the patient should continue treatment with the next scheduled dose. Patients will be given a paper treatment-compliance diary and will be asked to complete it on a daily basis. Patients must carry the diary with them at each Study Visit so as the data to be captured by the site investigative staff ([Table 6-1](#) and [Table 6-3](#)).

Patients will not take the morning dose of INC424 on the Study Days 1 and 15 for their timed PK assessment (see [Table 6-4](#)); study drug will be administered in the clinic in order to obtain post-dose plasma levels of INC424 ([Section 6.2.3](#)). On all other days corresponding to Study Visits, patients will take the morning dose of study drugs prior to the visit.

### **5.1.2 Dosing and treatment schedule**

INC424 tablets will be administered b.i.d. (approximately 12 hours apart: morning and night) orally, with at least 240 mL of any liquid, apart from alcohol, without regard to food, in an outpatient setting.

The dosage strength is 5 mg/tablet INC424 phosphate (free base equivalent). Patients will begin dosing on a b.i.d. schedule.

In the dose escalation phase, the starting dose will be 5 mg b.i.d. and the maximum dose will be 15 mg b.i.d., if MSSD is not reached at a lower dose. An adaptive Bayesian logistic regression model guided by escalation with overdose control will be used to allocate patients into each cohort. The dose-escalation cohorts will be: 5 mg q.AM / 5 mg q.PM, 5 mg q.AM / 10 mg q.PM, 10 mg q.AM / 10 mg q.PM, 10 mg q.AM / 15 mg q.PM, and 15 mg q.AM / 15 mg q.PM (see [Table 5-2](#)).

Following determination of the MSSD, a safety expansion phase will be conducted. Patients from both strata can be enrolled simultaneously during the safety expansion phase. If the MSSD is the same in both strata, all patients in the safety expansion phase will be treated with the same dose, regardless of the baseline PLT counts (see [Section 5.1.3](#)).

#### **5.1.2.1 Starting dose level for cycle 1**

INC424 will be dosed on a flat scale of mg/day (b.i.d.) and not individually adjusted by weight or body surface area. In the dose escalation phase of the study, the starting dose, for both strata, will be 5 mg q.AM / 5 mg q.PM. INC424 tablets of 5 mg are available.

#### **5.1.2.2 Dose escalation levels**

**Table 5-2 Dose levels**

Dose levels	
Dose level 1	5 mg q.AM / 5 mg q.PM
Dose level 2	5 mg q.AM / 10 mg q.PM
Dose level 3	10 mg q.AM / 10 mg q.PM
Dose level 4	10 mg q.AM / 15 mg q.PM
Dose level 5	15 mg q.AM / 15 mg q.PM

Doses will be administered according to the dose escalation schedule listed in [Table 5-2](#). Dose escalation will continue until MSSD is reached.

### **5.1.2.3 Criteria for dose escalation and determination of MSSD**

The primary analysis method is an adaptive Bayesian logistic regression model guided by escalation with overdose control ([Babb 1998](#)). To make decisions about escalation to the next dose level, the Investigators and the Sponsors study personnel (including the study physician, a safety physician and a statistician) will evaluate the available clinical and laboratory data (of all patients participating in the study, in all dose levels regardless duration), the toxicity information (including adverse events that are not DLTs) and the recommendations from the BLRM at a dose-escalation decision meeting or teleconference (T/C). Regarding thrombocytopenia, not only absolute PLT values, but also the speed at which the PLT counts decline will be taken into account for dose-escalation or dose-modification decisions. PK analysis data will not be a factor considered during this dose escalation decision process. The meetings should be conducted according to Sponsors' Standard Operating Procedures and further details will be provided in the Study Manual. Both Sponsors' study personnel (Novartis Pharmaceuticals and Incyte Corporation) must be in agreement for dose-escalation decisions and/or MSSD declaration. Drug administration at the next dose level may not proceed until the Investigators receive written confirmation from the Sponsors that the results of the previous dose levels were evaluated and it is safe to proceed to a higher dose level.

Criteria for dose escalation are provided in the [Section 3.1](#) and [Section 9.4.2](#). The MSSD will be the dose level most closely associated with a posterior DLT probability of between 16% and 33% that does not also have a greater than 25% probability of excessive toxicity.

In case the MSSD cannot be established due to lack of toxicity at the dose levels tested, the 15 mg b.i.d. dose will be the proposed dose for the patients in the safety expansion phase.

### **5.1.2.4 Dose escalation**

A prior distribution for the model parameters is derived based on experience with INC424 in adult patients in clinical study [\[INCB 18424-251\]](#), which was the dose-finding study in patients with myelofibrosis that preceded the pivotal phase III studies, [\[INCB 18424-351\]](#) and [\[INCB 18424-352\]](#) (see [Section 1.2.4](#)). The model will then be updated after each cohort of patients in each stratum with the DLT data from the current study. A detailed description of the methodology can be found in [Section 9.4.2](#).

The first 3 patients enrolled in the study must be enrolled from stratum 1 (patients with baseline PLT counts  $75-99 \times 10^9/L$ ). These 3 patients will be enrolled at the first dose level (dose level 1, [Table 5-2](#)). At least 3 evaluable patients are needed per dose level to make dose escalation decisions. The previously mentioned (see [Section 5.1.2.3](#)) BLRM with EWOC will be updated after all patients in a cohort become evaluable (for the dose-determining analysis set) or discontinue therapy. The dose-determining set (DDS), as defined in [Section 9.1.3](#), consists of all patients from the safety set who either (a) meet the minimum exposure criterion and have sufficient safety evaluations or (b) discontinue due to DLT. Decisions to escalate will be in accordance with satisfying the overdose control criterion based on the results of this modeling, and will be implemented after a joint teleconference or meeting between Investigators and Sponsors, as described in [Section 5.1.2.3](#). As an exception, if the first 2

patients in the cohort experience DLT before the enrollment of the 3rd patient, the model will be re-evaluated before enrollment of any additional patients to the cohort.

Enrollment will begin in stratum 1 at dose level 1. Once at least 6 patients from stratum 1 are confirmed to be in the dose-determining set (DDS) and dose level 3 is allowed for enrolment in stratum 1, then patients from stratum 2 (patients with baseline PLT counts 50-74 x10^9/L) may be enrolled at the first dose level. For the subsequent dose levels, patients in stratum 2 cannot be enrolled unless patients from stratum 1 have been allowed to be enrolled at 2 dose levels higher. Once the MSSD criteria have been met for stratum 1, stratum 2 can be independently further escalated, provided that this decision is supported by the BLRM with EWOC. Escalation for stratum 2 can be continued up to the dose level at which the MSSD criteria have been met for stratum 1, but not higher.

Dose escalation levels are listed in the [Table 5-2](#). A minimum of 9 evaluable patients must be treated at the dose declared to be the MSSD, for each stratum.

#### **5.1.2.5 Safety expansion phase**

Once the MSSD of INC424 is identified for both strata in the dose escalation phase of this study, additional patients will be enrolled and treated at this dose in order to further evaluate its safety and tolerability and to obtain estimates of efficacy, with the purpose of establishing that this dose is suitable for use in the low-platelet population of patients with MF. Patients from both strata can be enrolled simultaneously during the safety expansion phase. If the MSSD is identical in both strata, all patients in the safety expansion phase will be treated with the same dose. Prior to Amendment 4, twenty patients (10 patients from each stratum), in addition to the patients treated at the MSSD during the dose escalation phase, were to be evaluated during this part of the study. If the MSSD proves not to be well tolerated with further experience and via continuous update of the Bayesian logistic regression model during this safety expansion phase, then a lower dose may be evaluated to twenty additional patients (10 patients from each stratum).

With the approval of Amendment 4, all new patients enrolled to Stratum 1's safety expansion phase will be given the 10 mg BID dose, instead of the 15 mg BID dose level previously evaluated as the MSSD. This will allow 10 mg BID to be evaluated as the starting dose. Approximately 20 patients will be evaluated at this dose level in Stratum 1, inclusive of the patients already enrolled into this dose during the dose escalation phase, OR the Last Patient's First Visit (LPFV) will occur on 01 September 2017, whichever comes first. Patients already taking the 15 mg BID dose in Stratum 1's safety expansion phase will continue to take their assigned dose. Stratum 2 will maintain its original enrollment requirement of 10 patients at the MSSD.

The criteria for continuation of treatment and dose modification guidelines employed during the dose escalation phase will also be followed during safety expansion phase. Dose escalation above the MSSD will not be allowed.

#### **5.1.2.6 Dose cohort modification**

Dose level cohorts are listed in [Table 5-2](#). Possible changes in dose administration according to the BLRM include, but are not limited to, (a) expansion of the current dose group to further assess suspected treatment-related adverse events, (b) termination of any further escalation of

study drug. Investigators will receive written confirmation from the Sponsors notifying them that enrollment has been increased or decreased, or that no further enrollment will occur.

### 5.1.2.7 Intra-patient escalation

Intra-patient dose escalation will only be permitted after Study Day 56. During the course of the study, patients can be dose-escalated to the next higher dose level only once every two cycles (each cycle is 28 days), provided that ALL of the following criteria are met:

- inadequate efficacy is seen with the current dose level, as defined by observation of one or both of the following:
  - not achieving at least a 50% reduction in palpable spleen length compared to Study Day 1
  - lack of meaningful improvement in disease symptoms based on the Investigator's expert judgment.
- no treatment-related toxicity has occurred with the current dose level, resulting in treatment reduction or interruption or discontinuation in the previous 56 days.

For the first 24 weeks of treatment for an individual patient, the dose-escalation requirements will be as follows:

- the maximum dose with which the patient is to be treated does not exceed 15 mg b.i.d. and has been evaluated with at least 3 patients for a minimum of 28 days in that stratum, with no more than 1 out of 3 patients experiencing DLT
- the minimum PLT count during the first 24 weeks period is  $\geq 50 \times 10^9/L$  OR  $\geq 75\%$  of the baseline PLT count the current dose level is lower than the MSSD.

For treatment beyond the first 24 weeks, the dose-escalation requirements will be as follows:

- the maximum dose with which the patient is to be treated is the higher of: the MSSD established for that stratum OR 10 mg bid
- the minimum PLT count at the time of the escalation is  $\geq 50 \times 10^9/L$  AND is  $\geq 75\%$  of the baseline PLT count if a patient experienced a PLT count  $\leq 50 \times 10^9/L$  OR  $\leq 75\%$  of the baseline PLT count beyond the first 24 weeks, a dose escalation may be discussed with the sponsor. If a patient experiences a second episode of PLT count  $\leq 50 \times 10^9/L$  or  $\leq 75\%$  of the baseline PLT count (if it is suspected to be drug related), no further dose escalation will be allowed.

The rules for intra-patient escalation described above are also applicable to patients who have undergone one and only one dose reduction. Conversely, dose reduction rules (described in the [Section 5.1.3](#)) also apply to patients who undergo dose escalation. Once a patient undergoes a dose reduction due to treatment-related toxicity, the patient may not have a dose increase unless they have been on a stable dose for at least 28 days with no dose interruptions.

Patients who have experienced treatment-related  $\geq$  grade 3 toxicity of any nature aside from thrombocytopenia or grade 4 thrombocytopenia may not dose escalate a second time to the dose level at which this toxicity was seen.

For patients who undergo dose escalation, PLT counts must be obtained at least weekly for 4 weeks, and then at least every second week for the next 4 weeks. Thereafter, they may resume

monthly evaluations. Further recommendation can be given during the T/C meetings, on an individual basis.

Consultation with the Sponsors must occur prior to any intra-patient dose escalation.

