$\geq 75 \times 10^9 / L$ $50 - 74 \times 10^9 / L$ $35 - 49 \times 10^9 / L$ $25 - 34 \times 10^9 / L$ $< 25 \times 10^9 / L$	Continue at same dose level Continue at same dose level Continue at same dose level Continue at same dose level * Hold dosing  * qualifies as a DLT. If resolved to ≤ grade 2, resume therapy according to the rules of Table 5-6 .	Dose at the Time of the Platelet Decline 
 
 5 mg qd	5 mg b.i.d.	5 mg q.AM / 10 mg q.PM	10 mg b.i.d.	10 mg q.AM / 15 mg q.PM	15 mg b.i.d.	
 
 New Maximum Dose That Must be Instituted 
 
 Continue at same dose level	10 mg b.i.d.†	10mg b.i.d.†	
 
 Continue at same dose level	Continue at same dose level‡	
 
 Continue at same dose	5 mg b.i.d.	5 mg b.i.d.	5 mg b.i.d.	5 mg b.i.d.	
 
 5 mg qd	
 
 Discontinue	Hold dosing	
 
 †Patients from stratum 1 ‡Patients from stratum 2						5 mg qd	5 mg b.i.d.	5 mg q.AM / 10 mg q.PM	10 mg b.i.d.	10 mg q.AM / 15 mg q.PM	15 mg b.i.d.	Continue at same dose level			10 mg b.i.d.†	10mg b.i.d.†	Continue at same dose level			Continue at same dose level‡			Continue at same dose		5 mg b.i.d.	5 mg b.i.d.	5 mg b.i.d.	5 mg b.i.d.	5 mg qd	Discontinue	Hold dosing									
5 mg qd	5 mg b.i.d.	5 mg q.AM / 10 mg q.PM	10 mg b.i.d.	10 mg q.AM / 15 mg q.PM	15 mg b.i.d.																																					
Continue at same dose level			10 mg b.i.d.†	10mg b.i.d.†																																						
Continue at same dose level			Continue at same dose level‡																																							
Continue at same dose		5 mg b.i.d.	5 mg b.i.d.	5 mg b.i.d.	5 mg b.i.d.																																					
5 mg qd	5 mg qd	5 mg qd	5 mg qd	5 mg qd	5 mg qd																																					
Discontinue	Hold dosing																																									
In cases of grade 4 thrombocytopenia, follow-up rules according to Section 5.1.2.9.1 . For dose escalation or dose restart guidelines, see Table 5-5 and Table 5-6 .																																										

**Table 5-5 Dose escalation guidelines and allowed maximum doses for patients who have previously decreased dosing for thrombocytopenia**

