Current Platelet Count	Dose re-escalation guidelines (NOTE: maximum doses are given, lower doses may be used at Investigator's discretion)
25 x10  /L - 34 x10  /L	Continue at 5 mg qd until platelet counts $\geq$ 35 x10  /L
35 x10  /L - 49 x10  /L	Continue at 5 mg b.i.d. until platelet counts $\geq$ 50 x10  /L
$\geq$ 50 x10  /L	May increase dose by 5 mg qd each cycle (28 days) provided platelet count remains $\geq$ 50 x10  /L, up to the dose where platelet counts first declined and dose reduction occurred

**Table 5-6 Dose restart guidelines and allowed maximum doses for patients who have previously interrupted dose for grade 4 thrombocytopenia or grade 4 neutropenia**

Current platelet count	Dose restart guidelines (NOTE: maximum doses are given, lower doses may be used at investigator's discretion)
<35 x10  /L in a patient who is currently holding dose	Must continue to hold
35 - 49 x10  /L in a patient who is recovering from a dose hold	5 mg qd for 2 weeks, then increase in 5 mg qd increments, no faster than once every cycle (28 days), provided platelet counts $\geq$ 50 x10  /L
$\geq$ 50 x10  /L in a patient who is recovering from a dose hold	5 mg b.i.d. for at least 2 weeks, then may proceed with 5 mg qd dose increases, no more frequently than once every cycle (28 days), and provided platelets remain $\geq$ 50 x10  /L, up to the dose where platelet counts first declined < 25 x10  /L
Current ANC count	Dose restart guidelines (NOTE: maximum doses are given, lower doses may be used at investigator's discretion)
<0.75 x10  /L in a patient who is currently holding dose	Must continue to hold
0.75 – 1.00 x10  /L in a patient who is recovering from a dose hold	5 mg qd for 2 weeks, then increase in 5 mg qd increments, no faster than once every cycle (28 days), provided ANC counts $>$ 1.00 x10  /L
$>$ 1.00 x10  /L in a patient who is recovering from a dose hold	5 mg b.i.d. for at least 2 weeks, then may proceed with 5 mg qd dose increases, no more frequently than once every cycle (28 days), and provided ANC remain $>$ 1.00 x10  /L, up to a maximum dose of 5 mg qd BELOW the dose where ANC counts first declined < 0.50 x10  /L

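### In the first 24 weeks, section 5.1.2.7 lets some Stratum 2 patients on 5 mg b.i.d. step up at platelet counts of 38–49, where Tables 5-4 and 5-5 cap or hold the dose at 5 mg b.i.d.

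*Protocol*

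**What the plan says.** Counts below are in × 10⁹/L.

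**Protocol section 5.1.2.7, general conditions.** "Intra-patient dose escalation will only be permitted after Study Day 56", and "patients can be dose-escalated to the next higher dose level only once every two cycles". Efficacy must be inadequate. No treatment-related toxicity at the present dose level may have led to a reduction, interruption or discontinuation in the preceding 56 days. The sponsors must be consulted first.

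**Section 5.1.2.7, first 24 weeks.** The platelet condition is that "the minimum PLT count during the first 24 weeks period is" at least 50 or at least 75% of baseline. The same bullet runs on to say "of the baseline PLT count the current dose level is lower than the MSSD".

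**Section 5.1.2.7, beyond 24 weeks.** The condition changes to "the minimum PLT count at the time of the escalation is" at least 50 and at least 75% of baseline.

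**Section 5.1.2.7, patients already reduced.** "The rules for intra-patient escalation described above are also applicable to patients who have undergone one and only one dose reduction". Conversely, the reduction rules apply to patients who have been escalated.

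**Table 5-4, Day 29 onward, count 35–49.** The columns are headed "New Maximum Dose That Must be Instituted". Patients on 5 mg qd or 5 mg b.i.d. keep their dose. For all four higher regimens the entry is 5 mg b.i.d.

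**Table 5-5, for patients previously reduced for thrombocytopenia.** At 35–49 the entry is "Continue at 5 mg b.i.d. until platelet counts" of at least 50 are reached. At 50 or more, the dose may rise by 5 mg qd each 28-day cycle, up to the dose at which the count first fell and the dose was cut.

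**The concern.** The first-24-week test joins its two thresholds with OR, so whichever is lower governs. For the lower part of the Stratum 2 range, 75% of baseline is the lower one, and it falls inside the 35–49 band of both dose tables. An investigator following section 5.1.2.7 may raise the dose at a count where Table 5-4 does not allow the resulting dose and, for a previously reduced patient, Table 5-5 says to wait. Nothing in the protocol says which text prevails.

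At stake is consistent dosing of the patients with the fewest platelets. Two sites could treat the same count differently and both be compliant, and a step that is permitted on paper could need undoing at the next reading of the table.

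**Working it through.** The plan gives no figure to reproduce. The check is threshold arithmetic and a comparison of texts.

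**1. Effective threshold.** A ≥ 50 OR ≥ 75% rule is the same as: lowest count ≥ min(50, 0.75 × baseline). The two limits are equal at baseline 50 / 0.75 = 66.7.

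| Baseline | 0.75 × baseline | Whole counts below 50 that pass |
|---|---|---|
| 50 | 37.5 | 38–49 |
| 55 | 41.25 | 42–49 |
| 60 | 45 | 45–49 |
| 65 | 48.75 | 49 |
| 66 | 49.5 | none |
| 67 | 50.25 | none |
| 75–99 (Stratum 1) | 56.25–74.25 | none |

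**2. Extent.** Stratum 2 baselines are 50–74, which is 25 whole numbers. Those with at least one passing count below 50 are 50–65, which is 16 of 25 (64%). Across them there are 104 baseline/count pairs below 50 that pass. Under the AND form used beyond 24 weeks there are none.

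**3. Where the counts fall.** Every passing count below 50 lies in 38–49, inside the 35–49 row of both tables.

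**4. Never-reduced patient.** Baseline 60, lowest and current count 45, on 5 mg b.i.d., efficacy inadequate, after Day 56. Since 0.75 × 60 = 45, section 5.1.2.7 permits 5 mg/10 mg. At 45, Table 5-4 leaves 5 mg b.i.d. unchanged but gives 5 mg b.i.d. as the maximum for 5 mg/10 mg.

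**5. Once-reduced patient.** Start at 10 mg b.i.d. (the Stratum 2 MSSD, Amendment 4 rationale), baseline 56, so 0.75 × 56 = 42. The count is 45 on Day 43 and Table 5-4 takes the dose to 5 mg b.i.d. On Day 100 the count is still 45 and has never been lower. The reduction was 100 − 43 = 57 days ago, so the 56-day condition has passed, as has the separate requirement for 28 days on a stable dose. Section 5.1.2.7 permits 5 mg/10 mg; Table 5-5 keeps the patient at 5 mg b.i.d.

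**6. Other conditions.**
- The 56-day condition refers to the present dose level, so it does not stop a patient simply continued on 5 mg b.i.d.
- The bar on a second escalation to a dose that caused toxicity covers grade 4 thrombocytopenia and grade 3 or worse toxicity of other kinds, not a count of 38–49 as such.
- Sponsor consultation carries no platelet threshold.

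**7. Step interval.** Section 5.1.2.7 allows one step per two cycles (2 × 28 = 56 days). Table 5-5 allows one per 28 days at counts of 50 or more. Section 5.1.2.7 applies itself to once-reduced patients, and section 5.1.3 sends patients whose platelets have recovered to Table 5-5. This mismatch does not depend on steps 1–5 and can arise in either stratum.

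**The case against.** The strongest reply is that the texts measure different things. Section 5.1.2.7 tests the lowest count in the period, Table 5-4 the count at the time of decline, and Table 5-5 the current count. A patient with a nadir of 40 who has recovered to 60 meets section 5.1.2.7 and conflicts with neither 35–49 row. That stands, and it limits the point to patients whose current count is still 38–49. It does not remove it, because section 5.1.2.7 asks nothing of the current count before week 24.

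A reader might infer that such a patient must already be reduced at the count that permits escalation. The documents do not say so: at 35–49 a patient on 5 mg b.i.d. keeps the dose, and the cap applies only once a higher regimen is given.

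A reader might also infer that repeated steps up and down inflate the tolerability summaries. SAP section 2.2.2 summarises the number and percentage of subjects with a reduction or interruption, so a subject enters once however many reductions follow. The MSSD analysis is untouched as well: the DLT window closes at Day 28 and escalation opens only after Day 56.

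The change from OR to AND at week 24 is not an error in itself; Amendment 1 set separate escalation conditions for the extension.

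On the step interval, Table 5-5 can be read as a platelet-recovery route and section 5.1.2.7 as an inadequate-efficacy route. That is a fair reading, but the protocol does not say which governs a once-reduced patient who qualifies under both.

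Safeguards exist. Sponsor consultation is mandatory, and platelet counts are at least weekly for four weeks after a step. They reduce the risk without settling which text prevails.

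**Conclusion.** The contradiction is real but narrow. It concerns Stratum 2 patients with a baseline of 50–65, in the first 24 weeks after Day 56, taking 5 mg b.i.d. with a current count of 38–49. There is no conflict once the count has recovered to 50 or more, and no conflict below 50 in Stratum 1 or for Stratum 2 baselines of 67–74. At baseline 66 no whole count qualifies.

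The figure of 16 in 25 is a share of baseline values and should not be read as a share of patients. Practical reach is probably small. At the January 2015 cut-off, 13 of 19 Stratum 2 patients had started at the MSSD, leaving 6 below it. Given the planned timing of the interim analysis, those 6 should be past week 24 or off treatment. Later Stratum 2 patients start at the MSSD, so from here on mainly patients reduced from it can be affected. The documents do not give the baselines or platelet courses needed for a count.

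Assumptions:
- Baseline lies within the stratum range. If it means the last pre-dose value (SAP section 2.1.3) and that value is below 50, the overlap widens; below 35 / 0.75 = 46.7 it reaches the 25–34 row.
- The 35–49 row of Table 5-4 applies to a count found in that range, not only to a fresh fall. On the narrower reading, the Table 5-5 conflict for previously reduced patients still stands.
- The remaining conditions for the target dose, such as at least 3 patients evaluated in the stratum, are met.
- The break in the bullet before the MSSD condition was lost in layout; this does not affect the arithmetic.

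A possible further overlap in Stratum 1 at 50–74 is not claimed, because the relevant Table 5-4 cells are broken in the text available.

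**What to change.** Reconcile section 5.1.2.7 with Tables 5-4 and 5-5 so that:

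- no current count both permits an escalation and caps the dose below the level escalated to;
- the first-24-week test says whether it uses the lowest count in the period, the count at escalation, or both;
- one statement says which step interval applies to previously reduced patients, or which text governs where the two overlap.

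The clinical team chooses the rule; this review takes no view on which threshold, dose or interval is right. The cost is amendment wording and a note to sites. Sample size, the dose-toxicity model and the planned SAP summaries do not change.

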### **5.1.3 Dose modification and dose delay**

All dose modifications should be based on the worst preceding toxicity. Patients may be allowed dose reductions to 5 mg qd (dose level (-1)). Dose reductions more than one level at a time will not be allowed, except for thrombocytopenia, in which case different rules for dose reductions apply ([Table 5-4](#)). Note that the maximum allowed doses are quoted in the part of [Table 5-4](#) where guidelines for dose reduction due to thrombocytopenia are provided; lower doses may be used at investigator discretion. It is recommended that patients who are dose reduced for thrombocytopenia have more frequent hematology assessments. PLT counts must be obtained at least weekly for 4 weeks, and then at least every second week for the next 4 weeks. Thereafter, they may resume monthly evaluations.

Recovery of platelet counts will allow dose increases according to the guidelines in [Table 5-5](#). Note that once a dose is re-escalated, any subsequent declines in platelet count will require that [Table 5-4](#) be used to determine the new lower dose, or dose interruption.

Dose level (-1) is the lowest acceptable dosing level for a patient participating in the study. If a patient cannot tolerate dose level (-1), then he/she must be discontinued from study medication and withdrawn from the study (see [Table 5-2](#) for dose level definitions).

Dose modifications for toxicities occurring during the DLT-definition period (Study Day 1 through Study Day 28), and considered as treatment-related, will **not** be allowed until the toxicity qualifies as a DLT. After a toxicity event has been characterized as a DLT, a patient can resume therapy with a reduced INC424 dose according to the guidelines provided in the [Section 5.1.2.7](#). Dose modification recommendations after Study Day 28 are described in the [Table 5-4](#).

Any dose modifications must be recorded on the Dosage Administration Record eCRF.

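### Dose increases after platelet toxicity follow conflicting rules: two ceilings after a hold, and two paces and sets of conditions after a single reduction

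*Protocol*

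**What the plan says.** **After a hold for a count below 25 x10⁹/L.** Section 5.1.4 sends the patient to Table 5-6. With the count back at 50 or more, that table restarts at 5 mg b.i.d. for at least two weeks. It then allows steps of 5 mg/day, no more often than every 28 days, up to the dose at which the count dropped below 25. The note beneath the table says the maximum is always 5 mg/day below that dose, and it names platelets as well as ANC. The ANC row of Table 5-6 carries the same lower cap. Section 5.1.2.7 adds that certain patients, described as having had toxicity "aside from thrombocytopenia or grade 4 thrombocytopenia may not dose escalate a second time to the dose level at which this toxicity was seen".

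**After one reduction for platelets.** Two texts apply.

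- Section 5.1.2.7: "The rules for intra-patient escalation described above are also applicable to patients who have undergone one and only one dose reduction". The rules referred to require that "inadequate efficacy is seen with the current dose level" and set the pace: "During the course of the study, patients can be dose-escalated to the next higher dose level only once every two cycles". They also require that Day 56 has passed and that there has been no dose-modifying toxicity at the current level in the previous 56 days. In the first 24 weeks there is a platelet condition beginning "the minimum PLT count during the first 24 weeks period is" and continuing with 50 or more, or 75% or more of baseline. After a toxicity-related reduction, "the patient may not have a dose increase unless they have been on a stable dose for at least 28 days with no dose interruptions". Finally, "Consultation with the Sponsors must occur prior to any intra-patient dose escalation".
- Section 5.1.3: "Recovery of platelet counts will allow dose increases according to the guidelines in" Table 5-5. That table allows 5 mg/day more per 28-day cycle while the count stays at 50 or more, up to the dose at which the decline led to the reduction. It has no efficacy condition and no two-cycle spacing.

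**The concern.** Thrombocytopenia is this drug's main toxicity, and these are the rules for re-exposing patients who have just had it. After a hold, a site can find two different maximum doses in one table and its note. After a single reduction, one section forbids a step that another permits. In particular, a patient whose spleen and symptoms remain controlled at the reduced dose fails the efficacy condition of 5.1.2.7, yet may be stepped up under Table 5-5.

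The situation is not remote. Since Amendment 4, new Stratum 1 expansion patients start at 10 mg b.i.d., which is also the Stratum 2 MSSD. From Day 29, Table 5-4 cuts a 10 mg b.i.d. patient to 5 mg b.i.d. at a count of 35 to 49. What is at stake is consistent dosing after Day 28, including the dose in use at the Week 24 spleen assessment (a secondary endpoint).

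**Working it through.** The plan gives no figure of its own here, so the check is day counts and dose arithmetic on its rules.

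**1. Ceiling after a hold.** Inputs are the dose levels in Table 5-2, the Table 5-6 platelet row and the note under it. Row ceiling = held daily dose. Note ceiling = held daily dose − 5 mg.

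| Held at | Table 5-6 row | Note |
|---|---|---|
| 10 mg b.i.d. (20 mg/day) | 20 | 20 − 5 = 15 |
| 10/15 mg (25 mg/day) | 25 | 25 − 5 = 20 |
| 15 mg b.i.d. (30 mg/day) | 30 | 30 − 5 = 25 |

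The gap is 5 mg/day, or 25%, 20% and 16.7% of the held dose. The note says always and names platelets, so the row cannot be read as an exception to it.

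**2. Pace after one reduction, 5 to 10 mg b.i.d.** By Table 5-2 this is two steps (10 to 15 to 20 mg/day). Days needed = wait before the first step + spacing before the second. The 28 stable days of 5.1.2.7 are applied to both routes, because that sentence covers any dose increase after a toxicity-related reduction.

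- Table 5-5: 28 + 28 = 56 days at the least, longer if platelet recovery is later.
- 5.1.2.7, 28 stable days before step one: 28 + 56 = 84 days.
- 5.1.2.7, with the 56-day toxicity-free interval counted from the reduction: 56 + 56 = 112 days.

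The minimum under Table 5-5 is 28 to 56 days shorter (84 − 56; 112 − 56), and only 5.1.2.7 also requires inadequate efficacy.

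**3. Platelet condition in the first 24 weeks, Stratum 1.** For a baseline of 75 to 99, 75% is 0.75 × 75 = 56.25 to 0.75 × 99 = 74.25. Both exceed 50, so the either/or condition reduces to 50 or more. There are two readings:

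- Minimum means the lowest count in the period. Any count below 50 then bars escalation until Week 24, whatever the recovery.
- Minimum means the threshold to be met when the step is taken. The requirement is then 50, the same as Table 5-5, and there is no bar.

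The calculation assumes a baseline inside the stratum range. Below 50/0.75 = 66.7 the floor would fall under 50.

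**The case against.** The strongest reply is that Table 5-5 is the narrower rule. It covers only patients reduced for thrombocytopenia, and 5.1.3 points to it directly. The 5.1.2.7 sentence covers one reduction of any cause and can be read as saying only that a single reduction does not disqualify a patient from efficacy-driven escalation. Both tables are also permissive: they give maximum doses, so a site following the stricter rule breaks neither text, and the Sponsor must be consulted before any escalation. Much of this stands, and it is probably the intended reading. But the protocol does not say so, the 5.1.2.7 sentence has no platelet exemption, and consultation does not supply a single written rule. None of it touches the Table 5-6 ceiling.

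Some stronger readings are tempting but not supported:

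- **Stratum 1 is barred until Week 24, giving 20 against 10 mg/day at Day 168.** This needs the lowest-count reading. The parallel post-Week-24 condition uses the same word for a count at the time of escalation, where it can only be a threshold. Take a Stratum 1 patient cut from 10 to 5 mg b.i.d. on Day 57 with counts of 50 or more from Day 85. Under the threshold reading, the 84-day route reaches 20 mg/day on Day 57 + 84 = 141. The 112-day route is at 15 mg/day on Day 168, since 57 + 112 = 169.
- **Table 5-5 permits 10 mg b.i.d. in 28 days.** That takes the first step at recovery. If recovery comes before 28 stable days, it breaches the 5.1.2.7 stable-dose rule.
- **The 5.1.2.7 grade 4 sentence independently settles the ceiling.** It bars escalating a second time to the toxic level. A patient whose grade 4 event occurred at the starting dose has not escalated to that level even once, and the sentence is ambiguously worded.
- **The 14-day first step in Table 5-6 contradicts the 28 stable days.** This depends on whether a hold with a lower restart counts as a reduction. The protocol does not say, SAP Section 2.2.2 defines reduction and interruption separately, and 5.1.4 sends these patients to Table 5-6. Waiting 28 days also satisfies a minimum of two weeks.

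**Conclusion.** Two inconsistencies hold. The first is certain: the Table 5-6 platelet row and its note set ceilings 5 mg/day apart. The Amendment 3 rationale, which describes allowing restart up to the dose of first decline, suggests that the row was raised and the note left behind, but the note is still operative text. The second is a real gap in precedence: after one platelet-related reduction, 5.1.2.7 and Table 5-5 differ on the efficacy condition and on pace (at least 56 against 84 to 112 days for 5 to 10 mg b.i.d., with 28 stable days on both sides). A Stratum 1 bar before Week 24 follows only under the lowest-count reading.

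The consequences are limited to dosing after Day 28 and possibly the dose in use at Week 24. The DLT endpoint and the MSSD rest on Days 1 to 28 and are unaffected. The Amendment 4 rationale reports frequent reductions after cycle 1 in patients started at 15 mg b.i.d. but gives no count, so the number of patients affected cannot be computed.

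**What to change.** 1. **Set one platelet ceiling in Table 5-6.** By default use the cap in the note, which matches the ANC row. The cost is a ceiling 5 mg/day lower. The restart dose then needs a matching line for a patient held at 5 mg b.i.d., because 10 − 5 = 5 mg/day is below the 5 mg b.i.d. restart. If the Sponsor confirms the Amendment 3 ceiling instead, remove platelets from the note's cap and align the grade 4 sentence in 5.1.2.7.
2. **State precedence in 5.1.2.7.** Its conditions govern efficacy-driven escalation; re-escalation after a platelet reduction or hold follows Tables 5-5 and 5-6. Say that the 28-day stable-dose rule and Sponsor consultation apply to the first such step. The cost is up to 28 − 14 = 14 days' delay after a hold.
3. **Clerical.** Section 5.1.3, the Table 5-4 footnotes and Section 9.4.1 cite 5.1.2.7 where 5.1.2.8 is evidently meant; Section 3.1 cites 5.1.2.6 where 5.1.2.7 is meant.

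This is one wording amendment and a letter to sites. It needs no new data or visits.
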